A randomized clinical trial will enroll 40 participants. Cognitively healthy elderly adults, age 65-89 will undergo either a CT intervention in combination with optimized transcranial direct current brain stimulation (tDCS) or sham tDCS control. The CT intervention will employ a suite of adaptive training tasks from the POSIT Science Brain HQ²⁸¹; a well validated CT method for enhancing cognitive functioning in the elderly. Participants will receive tDCS or sham/placebo precision stimulation administered during training.

Participants will be assessed at baseline and after CT (2 weeks). At each time point, a comprehensive neurocognitive, clinical and multimodal neuroimaging assessment of brain function, metabolic state, and brain structure will be conducted.

FMRI will be used to assess brain response during working memory, attention and memory encoding. Proton magnetic resonance spectroscopy (MRS) will assess cerebral metabolites, including gamma-aminobutyric acid (GABA) concentrations, sensitive to neural plasticity in task-associated brain regions.

The central hypothesis of this proposal is that optimized tDCS will increase neural plasticity in task associated brain regions, facilitating effectiveness of CT and transfer to everyday function.

Aim 1. Determine whether neurocognitive improvement and longer-term functional outcome (as measured by “ecological assessment”) are better when CT is coupled with tDCS, an intervention that will increase neural plasticity and augment training effects.

H1.1. Active tDCS combined with CT will amplify effects of CT on measures of attention, working memory, executive functioning, and learning efficiency, while sham tDCS will not.

H1.2. Active tDCS will enhance near and far transfer of CT, but sham will not evidence near or far transfer.

Aim 2. Determine whether CT combined with tDCS leads to greater functional and metabolic brain changes (fMRI, MRS). Effects will parallel Aim 1.

H2.1. Combined CT + tDCS will potentiate decrease activation in working memory and attentional (dorsolateral prefrontal cortex, medial frontal cortex, inferior parietal lobe, supplementary motor association cortex) brain systems, reflecting increased neural efficiency, while CT + sham tDCS will not.

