tDCS. Brain stimulation provides a means of directly augmenting CT effects. tDCS was selected from possible alternatives (e.g., transcranial magnetic stimulation) based on research and data by [name] (PI), [name], and [name] (consultants), including its safety profile, ability to facilitate neural plasticity, and potential for application outside of research settings. Recent work from our lab has demonstrated that MRI-derived computational models of tDCS-induced current intensity reaching a specific brain region important to stimulation gains can reliably predict individual treatment response to tDCS (Albizu et al., 2020). Leveraging this information, we can determine the optimal dosing strategy to maximize the likelihood of treatment response on an individual level. Thus, the location of electrodes where electrical current is applied and the level of current intensity (up to 4mA) will vary depending on the individual anatomy of each participant. Further, stimulation precision will be enhanced by stereotactic neuronavigation system (6.5) as a real-time guidance to ensure accurate and consistent placement of tDCS electrodes. These stimulation parameters have been used in previous studies (Khadka et al., 2020; Shinde et al., 2021; Workman, Fietsam, & Rudroff, 2020) and, to date, the use of conventional tDCS protocols in human trials with parameters ≤ 40 min, ≤ 4.0 mA, and ≤ 7.2 Coulombs has not produced any reports of a Serious Adverse Effect or irreversible injury ([name] et al., 2016). Theoretical issue damaging levels have been estimated to be 25 mA/cm 2 and 216 C/cm 2 (Sundaram et al., 2009). The current study applies well below these levels with 0.114 mA/cm 2 of current density and 0.137 C/cm 2 of total stimulation charge.

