commercially available (www.positscience.com), with well-documented protocols/manuals (See Appendix 1) and thus not described in detail here. (See miscellaneous attachments for specific game descriptions.) Hardware: Participants will complete CT on computers located at the McKnight Brain Institute. Support: Participants will have the opportunity to ask questions, and will be instructed on the various computer tasks. No special technical skills or experience are required. A support phone number will be available if participants have questions that arise between study visits.

6.5. Transcranial Direct Current Stimulation:

Optimized tDCS: Based on our well-established artificial intelligence/computational modeling workflow (see figure below), stimulation parameters will be optimized per participant to maximize the likelihood of treatment response (Albizu et al. 2021). A Soterix Clinical Trials Direct Current Stimulator will apply 20 minutes of up to 4.0mA direct current through two biocarbon rubber electrodes covered with at least 5mm-thick conductive electrode paste buffer, and placed over the optimized locations based on the international 10-20 system by using a combination of 10-20 EEG cap measurement . Impedance quality will be $\leq 10\text{k}\Omega$ to insure proper stimulation of brain tissue.

Sham tDCS: Sham stimulation is performed with the same device and all procedures will be identical except for the duration of stimulation. Participants will receive 30 seconds of 2 mA of direct current stimulation at the beginning of the session. Participants habituate to the sensation of tDCS within 30-60 seconds of stimulation. This procedure provides the same sensation of tDCS without the full duration of stimulation, making it a highly effective sham procedure. Blinding: The device has built in RCT double blinding protocols. Soterix will communicate only with [name] to de-identify data for analyses.

Physiological Recording: During stimulation sessions participants will be asked to wear a special wristband that will be used to record physiological information such as pulse.

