Exclusion criteria: 1) Neurological disorders (e.g., dementia, stroke, seizures, traumatic brain injury). 2) Evidence of dementia (NACC UDS scores of 1.5 standard deviations below the mean for age, sex and education adjusted norms in a single cognitive domain on the task). 3) Past opportunistic brain infection 4) Major psychiatric illness (schizophrenia, intractable affective disorder, current substance dependence diagnosis or severe major depression and/or suicidality. 5) Unstable (e.g., cancer other than basal cell skin) and chronic (e.g, severe diabetes) medical conditions. 6) MRI contraindications (e.g., pregnancy, claustrophobia, metal implants that are contraindicated for MRI). 7) Physical impairment precluding motor response or lying still for 1 hr and inability to walk two blocks without stopping. 8) Certain prescription medications may possibly reduce effects otherwise induced by the tDCS stimulation protocol, and are listed on a Drug Exclusion List attached to the Appendices in Miscellaneous attachments of this study. 9) Hearing or vision deficits that will not allow for standardized cognitive training stimulation; ie colorblindness, inability to hear through headphones (with or without hearing aids), macular degeneration or other significant diseases that cause severe loss of vision. If vision is corrected with lenses to appropriate levels, then participant will be eligible. 10) Left handedness, as those with

left-handedness have a higher percentage rate of atypical functional lateralization for brain functions, which would significantly interfere with interpretability of brain data. 11) Participants with precision tDCS dosage of >4.0mA required will be excluded due to limitations of tDCS device (maximum output of 4.0 mA). The maximum output of 4.0 mA reflects a technical limitation of the device design rather than a safety threshold.

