Protections of risks related to study questionnaires. To minimize any risks related to emotional responses to questionnaires, persons will be informed about the types of questions included in the surveys, which are similar to the types of questions persons might be asked by their doctor in a clinical setting.

Protection of risks related to tDCS. To minimize risk associated with tDCS, participants will be monitored throughout stimulation sessions and asked to report any discomfort. If scalp sensation is uncomfortable, stimulation levels will be decreased to a comfortable level or will be stopped. In the event of a headache, stimulation will be decreased to a comfortable level (where the headache or nausea is no longer present) or will be stopped. All tDCS sessions will be administered and continually supervised by a trained experimenter. The above symptoms have only been reported when participants are actively being stimulated. However, to assess for any symptoms occurring during the interval between stimulation sessions, we will administer a brief symptom screening questionnaire at the beginning (symptoms in the past 24 hours) and end of each session (symptoms during stimulation). tDCS has not been shown to cause seizures nor lower the seizure threshold in animals. There are no reports of seizure induced by tDCS in human participants in the literature. However, this may not be true for epilepsy patients, whose seizure threshold rates are likely abnormal. Prior history of neurological disorders is an exclusionary criterion for our study and thus no participants will have a history of seizure.

Protection against risks associated with neuroimaging. MRI is widely regarded as a safe, noninvasive procedure for visualization of brain tissue in both adults and children. Prior fMRI studies by our group and by other groups document the innocuous nature of these procedures. Prior to study participation, all participants will be informed of the MRI procedure during the informed consent/assent process. The proposed study will be performed on an FDA approved Siemens 3 Tesla scanner located at the Advanced Magnetic Resonance Imaging and Spectroscopy (AMRIS) research facility at UF. There are no known long-term effects of MRI procedures on the body. The FDA Information Sheets, Food and Drug Administration, October 1995, p. 79, lists as a non-significant risk device, "Magnetic Resonance Imaging (MRI) Devices within FDA-specified

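### Sham is fixed at 2 mA while active current is individualised up to 4.0 mA, so the arms do not differ in duration alone as Section 6.5 states

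*Combined protocol and SAP*

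**What the plan says.** Section 6.5 (Sham tDCS) says of the control condition that "all procedures will be identical except for the duration of stimulation". The next sentence sets its dose: "Participants will receive 30 seconds of 2 mA of direct current stimulation at the beginning of the session". The same paragraph goes on to claim: "This procedure provides the same sensation of tDCS without the full duration of stimulation". It supports this by saying that people get used to the sensation within 30 to 60 seconds.

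The active arm is described just above. The stimulator "will apply 20 minutes of up to 4.0mA direct current", with parameters chosen for each participant by the modelling workflow. Section 6.2.1 (tDCS) confirms that "the level of current intensity (up to 4mA) will vary depending on the individual anatomy of each participant".

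Three other places bear on the point:

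- Section 5: "Participants will receive tDCS or sham/placebo precision stimulation administered during training".
- Section 7, exclusion criterion 11: "Participants with precision tDCS dosage of >4.0mA required will be excluded due to limitations of tDCS device". The criterion is not limited to one arm.
- Section 7, protection of risks related to tDCS: the current is lowered or stopped if scalp sensation is uncomfortable. On symptoms, "we will administer a brief symptom screening questionnaire at the beginning" and again at the end of each session.

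A tDCS sensation questionnaire is given on each training day (Section 6.1 table; Section 6.7), and a questionnaire on expectations of brain stimulation at both assessments (Section 6.7). The documents name no treatment guess and no comparison of blinding by arm.

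**The concern.** A sham described as differing only in duration should start at the same current as the active condition. This one starts at a fixed 2 mA, while the active current varies with anatomy. The sham specification would be accurate for the conventional 2 mA protocol that Section 4.3.5 gives as an example, but this trial's active arm deliberately departs from that protocol.

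The plan relies on matched sensation when it calls the sham highly effective. Its own safety procedure treats sensation as depending on current, because it turns the current down when sensation is uncomfortable. Current at onset is the quantity that differs between the arms.

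At stake is the reading of the active-versus-sham contrast, the only randomised comparison of stimulation in the trial. Cognitive test scores (Aim 1) are the outcomes most open to expectancy if participants can tell which condition they received; metabolite concentrations from spectroscopy are less exposed. As the plan stands, a report would describe a duration-only sham that was not delivered.

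**Working it through.** **Inputs.** Active: up to 4.0 mA for 20 min = 1200 s (6.5). Sham: 2 mA for 30 s (6.5). Stated densities: 0.114 mA/cm² and 0.137 C/cm² (6.2.1). The distribution of optimised doses is not given, nor is a lower limit, so 1 to 4 mA is used as an illustrative range.

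**Step 1: reproduce the plan's dose figures.** Charge density = current density × time = 0.114 mA/cm² × 1200 s = 137 mC/cm² = 0.137 C/cm². This agrees with Section 6.2.1 and needs no electrode area.

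The documents do not state an electrode area. If the stated density refers to 4.0 mA, the area is 4.0 / 0.114 = 35.1 cm². If it referred to 2 mA, the area would be 2 / 0.114 = 17.5 cm². The 4.0 mA reading is assumed wherever 35 cm² is used below.

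**Step 2: current and charge by optimised dose I.** Current ratio = I / 2. Active charge = I × 1200 s. Fixed sham charge = 2 mA × 30 s = 0.06 C. A sham differing only in duration would deliver I × 30 s.

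| Optimised dose | Active/sham current | Active charge | Charge ratio, sham fixed at 2 mA | Charge ratio, sham at own dose |
|---|---|---|---|---|
| 1 mA | 0.5 | 1.2 C | 20 | 40 |
| 2 mA | 1.0 | 2.4 C | 40 | 40 |
| 3 mA | 1.5 | 3.6 C | 60 | 40 |
| 4 mA | 2.0 | 4.8 C | 80 | 40 |

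The arms match in current only at 2 mA. At the ceiling, the 80-fold charge ratio is 40 (1200/30, the intended duration difference) × 2 (4/2, the unstated current difference). On 35 cm², current density at the ceiling is 0.114 mA/cm² for active against 2/35 = 0.057 mA/cm² for sham. The 2:1 ratio does not depend on the area.

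**Step 3: does another part of the plan equalise the currents?** No. The Section 5 phrase about sham precision stimulation may mean electrode location only, and it does not override the explicit 2 mA. Lowering current for discomfort is a reaction to a complaint and does not match the arms. The sensation questionnaire measures a difference without removing it.

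**Step 4: is a matched sham within reach?** Criterion 11 applies to all participants, which implies that a precision dose is calculated for each of them, including those given sham. A sham at that dose delivers at most 4 mA × 30 s = 0.12 C, which is 0.12 / 4.8 = 2.5% of the active charge at the same dose.

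**Step 5: what a treatment guess could show.** With 40 guesses, 20 correct (50%) has an exact (Clopper-Pearson) 95% interval of 33.8% to 66.2%. The smallest count whose interval excludes 50% is 27 of 40 (50.9% to 81.4%); 26 of 40 gives 48.3% to 79.4%. Within an arm of 20 (equal arms assumed), 10 correct gives 27.2% to 72.8%. Such an item can only be descriptive.

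**The case against.** The strongest reply is that this is a conflict of wording with no demonstrated effect on blinding. Each participant receives one condition and cannot compare the two. Active current varies between people, so no single sensation marks the active arm. The plan's argument for the sham is habituation, and sensation that continues through 20 minutes may be a stronger cue than onset strength; matching the current would not remove that cue. The number of participants away from 2 mA is unknown, and most of the charge ratio is the intended duration difference.

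Much of this stands as a limit on the consequence. Failed blinding is not shown, and no bias can be given in standard deviation units. But habituation concerns how long sensation lasts, not how strong it is at onset, so it does not support a claim of equal sensation at different currents.

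Other points are fair in part. The timing of dose modelling relative to randomisation is not stated, nor is the capability of the device's sham mode, so feasibility is likely but not established. The questionnaire items are not shown, so one can say only that no guess item is named. The trial is a pilot of 40, and the plan sets out little analysis for any outcome, so the missing blinding comparison is secondary to the sham specification. None of this makes the duration-only statement correct.

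**Conclusion.** The concern holds. The duration-only description is wrong for every optimised dose other than 2 mA, and the equal-sensation claim is unsupported at those doses. The mismatch reaches a factor of 2 in onset current at the 4.0 mA ceiling and would reverse for any dose below 2 mA.

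Confidence is high for the contradiction, which rests on the wording of Sections 6.5 and 6.2.1 alone. The effect on blinding is uncertain: it depends on the unreported dose distribution and on whether participants perceive the difference. The correction should be made because it is cheap and concerns the control condition of the main comparison.

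**What to change.** **Preferred.** Deliver sham for 30 seconds at the participant's own optimised current and electrode locations, and say so in Section 6.5. Duration is then the only difference, as the plan intends.

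**If 2 mA is kept.** Delete the duration-only and equal-sensation statements, and report the intensity difference as a limitation.

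**In either case, as descriptive additions:**

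- Compare the daily sensation ratings and per-session symptom ratings by arm.
- Log reductions in current by arm.
- Consider one forced-choice arm guess with a confidence rating, for participant and operator, reported by arm against 50%. A guess after the last session may also reflect perceived improvement.

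**Cost.** One corrected sentence and a per-participant sham setting, using a dose that criterion 11 already implies. Whether the sham mode accepts an individual current must be checked with the manufacturer, in a way that keeps the double blind. At the ceiling, sham charge doubles from 0.06 to 0.12 C and onset discomfort may rise. The additions need a log field, a guess item with confidence rating and one table by arm. A documented blinding failure would weaken the trial's conclusion.
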